6.2.2 Missing values for outcomes

Specific imputation methods will not be used for outcome variables. However, for descriptive analyses, each variable will be described with frequencies of missing and “Not Known” values, where applicable.

Other methods, including complete case analysis, will be considered when appropriate. For ‘time-to-event’ outcomes, patients who are lost to follow-up prior to the time point of interest will be censored.

6.3 Descriptive analyses

Prior to implementing the analysis to address the primary objectives of the study, descriptive analyses will be carried out to understand the main features and patterns in the population and in the data collected. Study population characteristics will be tabulated at index date.

WHO Ordinal Scale for Clinical Improvement (see Appendix 1) scores distribution over time will be displayed. Kaplan-Meier estimates will be calculated, and curves plotted for each time-to-event outcome.

The observed incidence weekly rates of PCR-confirmed or symptomatic COVID-19 and of COVID-19-related hospitalizations and deaths will be tabulated over weeks by facilities and compared according to

prophylactic treatment use (yes/no; by treatment, subject to sufficient sample size; and by pre- and post-exposure (to COVID-19 patients) use, subject to sufficient sample size).

Applications of estimated propensity scores will be employed to explore differences between HCWs' profiles exposed versus non-exposed to potential prophylactic treatments. Propensity scores will be estimated for receipt of potential prophylactic treatments based on key covariates of interest for the HCWs' profiles (age, gender, race, type of HCW, BMI, smoking status, medical history). Estimated propensity score distributions will be displayed over weeks and a concordance analysis performed to detect any trend over time.

Stratified pooled analyses at country level will also be displayed.

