8.7.3 Descriptive Analyses

Prior to implementing the analysis to address the primary objectives of the study, descriptive analyses will be carried out to understand the main features and patterns in the population and in the data collected.

Crude numbers for each outcome will be displayed over time and as cumulative risks.

Study population characteristics will first be tabulated at index date and over time. Likewise, variables measuring exposure to potential prophylactic treatment and to COVID-19 patients over time.

Continuous variables over time will be described using summary statistics including mean, median, minimum and maximum, as well as box plots. Scores distribution over time will be displayed and Kaplan-Meier estimates will be calculated, and curves be plotted for each time-to-event outcome.

The observed incidence weekly rates of PCR-confirmed symptomatic COVID-19 and of COVID-19-related hospitalizations and deaths will be tabulated over weeks by facilities and compared according to prophylactic exposure in the study or against comparative controls.

Applications of estimated propensity scores will be employed to explore differences between HCWs' profiles exposed versus non-exposed to potential prophylactic treatments. Estimated propensity score distributions will be displayed over weeks and a concordance analysis performed to detect any trend over time.

Stratified pooled analyses at country level will also be displayed.

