8.7.4 Primary Analysis

A standard pharmaco-epidemiological inferential analysis will be conducted treating the registry data as a cohort with dynamic exposure to both prophylactic treatment and to COVID-19 infected patients and adjusting for potential confounding.

Both crude and adjusted hazards ratios will be estimated for prophylactic regimens of interest and any observed impact on the risk of infection among HCWs based on all statistical inferential models will be reported.

Outcomes will be adjudicated to exposure time based on prior decision rules agreed with the SAC. Hazards for each subject-week will be compared and adjusted for exposure to prophylaxis over time, exposure to COVID-19 positive patients over time and to other covariates, accounting for subject-level clusters. Repeated time-to-event analyses with competing risk will be carried out.

Handling of missing data and unexplained drop-outs will be discussed with the SAC. Interaction terms to be considered will also be discussed with the SAC and clinicians.

Matching or other balancing methods such as estimated propensity score matching, inverse probability weighting or marginal structural methods, or alternative methods, will be considered to potentially address the identified biases and allow for evaluation of association.

In case the number of infection cases is lower than anticipated to allow for such analyses, matched case-control analyses will also be considered.

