6.5 Secondary analysis

All time-to-event secondary analyses will be conducted similarly as for the primary analysis. They include:

- Time to clinical events (each defined by the WHO severity score or proxies to be defined)
 - Ambulatory status with no limitation of activities (WHO Ordinal Scale classification 1). This will be defined as subjects reporting COVID-19 related symptoms, clinical diagnosis of COVID-19 or positive test results, but reporting “No” limitation of activities due to their symptoms and no hospitalisation.
 - Ambulatory status with limitation of activities (WHO Ordinal Scale classification 2). This will be defined as subjects reporting COVID-19 symptoms, clinical diagnosis of COVID-19 or positive test results and reporting “Yes” to having their usual activities limited being limited due to their symptoms, but no hospitalisation.
 - Hospitalised mild disease (WHO Ordinal Scale classifications 3 and 4). This is defined as being hospitalised without being admitted to the ICU or without ventilation.
 - Hospitalised severe disease (WHO Ordinal Scale classifications 5 to 7). This is defined as being hospitalised with either admittance to the ICU and/or receiving ventilation.
 - Death (WHO Ordinal Scale classification 8)

Furthermore, to explore key factors (eg. PPE, HCW and healthcare facility characteristics, underlying co-morbidities, household history and COVID-19 exposure) that potentially modify the risk of COVID-

19 among HCWs, the following analysis will be undertaken. For the covariates remaining in the final model of the primary analysis, one covariate will be removed at a time and will be tested using a likelihood ratio test to determine their association with the primary outcome.

Finally, as described in section 3.5.2, the type of prophylactic treatments (Chloroquine, Hydroxychloroquine, Azithromycin, Lopinavir/ritonavir, Ivermectin, others) will be characterized by dose, frequency and duration, overall and by country/region/site. To note, prophylactic treatment use will be defined by relevant indication from 'prophylactic treatment' section of the survey; in addition, if there is an indication of drugs in 'concomitant medications' section that are also listed but not selected under 'prophylactic treatment' section, those indications will be added too.

Other derived variables such as time in hospitalization will be analyzed via generalized mixed effect models.

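### The SAP plans Kaplan-Meier curves for the severity states, omits the competing-risk analysis that the protocol promises, and does not say how a worker who reaches another state or dies is handled

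*SAP*

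**What the plan says.** SAP 6.3 sets one descriptive method for all event times: "Kaplan-Meier estimates will be calculated, and curves plotted for each time-to-event outcome". SAP 6.5 lists five clinical events as time-to-event outcomes (ambulatory without limitation, ambulatory with limitation, mild hospitalisation, severe hospitalisation, death) and adds "All time-to-event secondary analyses will be conducted similarly as for the primary analysis".

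The definitions in SAP 6.5 decide which states can coexist:

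- Ambulatory, not limited: "limitation of activities due to their symptoms and no hospitalisation".
- Ambulatory, limited: "limited being limited due to their symptoms, but no hospitalisation".
- Mild hospitalisation: "This is defined as being hospitalised without being admitted to the ICU or without ventilation".
- Severe hospitalisation: "This is defined as being hospitalised with either admittance to the ICU and/or receiving ventilation".
- Death is all-cause (SAP 3.5.2).

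Protocol 8.7.4 states "Repeated time-to-event analyses with competing risk will be carried out", and Protocol 8.7 leaves detailed methods to the SAP. The SAP's only time-to-event model is the mixed-effect Cox regression of 6.4.1. It mentions no competing risk, cumulative incidence function or multi-state method. The SAP is based on protocol version 1.0, but the amendment log lists no change to the competing-risk sentence, so the version gap does not explain the omission. SAP 6.2.2 names loss to follow-up as the reason for censoring and is silent on HCWs who enter a different state or die.

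**The concern.** Both ambulatory states require no hospitalisation and are told apart by a yes/no answer, so on any one classification an HCW can be in only one of them and in neither hospitalised state. Death ends data collection (Protocol 8.6.1, SAP 3.1) and prevents every later event. If a Kaplan-Meier curve for one state censors HCWs who reached another, it treats them as still able to have the event. One minus that curve then exceeds the proportion who actually reach the state.

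Protocol 8.7.3 wants outcomes shown as cumulative risks, which is the quantity affected. The relative error grows with total infection risk, so it can differ between countries, facilities and prophylaxis groups. The state curves would also fail to reconcile with the infection curve. Because the SAP gives no rule, two analysts could draw different curves from the same text.

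**Working it through.** **Inputs.** From SAP section 5 and Protocol 8.7.7: N = 10,000, 20% unexposed, 10% infection risk if unexposed, relative risk 0.78, 80% power. From SAP 6.1: two-sided 5%. The documents give no severity split and no infection risk above 10%; those used below are assumptions.

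**The plan's own figure.** Expected infections are 2,000 × 0.10 + 8,000 × 0.078 = 200 + 624 = 824, an overall risk of 8.24%. The Schoenfeld formula gives √(824 × 0.2 × 0.8) × |ln 0.78| − 1.96 = 11.48 × 0.2485 − 1.96 = 0.89, which is 81.4% power against the stated 80%. A pooled two-proportion calculation gives 87.7%. The rest of the check uses only the infection risks.

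**Formula.** Let F be total infection risk and s a state's share of infections, with proportional cause-specific hazards.

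- True cumulative incidence: s × F.
- One minus Kaplan-Meier, other states censored: 1 − (1 − F)^s.
- Because 1 − e^(−x) ≤ x, the summed Kaplan-Meier risks cannot exceed −ln(1 − F), and no state's relative excess can exceed −ln(1 − F)/F − 1.

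**At F = 10%.** The limit is −ln 0.9 = 10.54%, so the summed excess is at most 0.54 points and the relative excess at most 5.4%.

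| Assumed split | Sum of 1 − KM | Excess (points) |
|---|---|---|
| 80/15/4/1 | 10.18% | 0.18 |
| 60/30/7/3 | 10.29% | 0.29 |
| four equal shares | 10.40% | 0.40 |

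Across these splits each state is overstated by 1.0% to 5.3% relative. At the overall risk of 8.24% the excess is 0.12 to 0.27 points, with a limit of 0.36.

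**At F = 40%, split 60/30/8/2 (both assumed).**

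| Share | 1 − 0.6^s | s × 0.40 | Relative excess |
|---|---|---|---|
| 0.60 | 26.4% | 24.0% | 10% |
| 0.30 | 14.2% | 12.0% | 18% |
| 0.08 | 4.0% | 3.2% | 25% |
| 0.02 | 1.0% | 0.8% | 27% |
| Sum | 45.6% | 40.0% | 14% |

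In absolute terms the largest error falls on the commonest state (2.4 points); the rarest is out by about 0.2.

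**Dependence on the censoring rule.** A simulation of 1,000,000 HCWs over 12 weekly steps (split 60/30/7/3) gives:

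| Target F | Infected | Sum, other states censored | Sum, other states kept at risk to week 12 |
|---|---|---|---|
| 10% | 10.04% | 10.30% | 10.04% |
| 50% | 49.98% | 58.7% | 49.98% |

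With HCWs kept in the risk set, and no other censoring, there is no overstatement.

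**Effect on a group comparison at design values.** With the same split in both groups, the distortion for a very rare state tends to ln(1 − 0.078)/ln(1 − 0.10) = 0.0812/0.1054 = 0.771, against a true ratio of 0.78.

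**The case against.** The strongest reply is that the bias depends on a reading the SAP does not contain. A reader might infer that the planned curves will certainly be too high. The documents do not support that: SAP 6.2.2 censors loss to follow-up only, and keeping HCWs in the risk set removes the excess. This stands, so the bias is conditional. It does not remove the gap, because observation ends at death and keeping the dead at risk would need an explicit rule.

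Second, a reader might take any sum above the total infected as proof of Kaplan-Meier error. It is not. Status is reported weekly, so an HCW may be ambulatory one week and hospitalised later. The mild definition, with its alternative of no ventilation, overlaps the severe one for an ICU patient who is not ventilated. Death is all-cause. Risks of ever reaching each state can properly add to more than the total infected. For the same reason, making every other state a competing event would drop HCWs who are first ambulatory and later hospitalised, and would understate hospitalisation.

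Third, shell Table 8.2.2 reports each severity state as a simple count and percentage, which does not carry this error, so not every reported severity risk is at stake.

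Fourth, Kaplan-Meier is not itself a departure from the protocol, since Protocol 8.7.3 says "Kaplan-Meier estimates will be calculated, and curves be plotted for each time-to-event outcome". What the SAP drops is the competing-risk analysis of 8.7.4.

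All four points narrow the concern. None supplies the missing method or rule.

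**Conclusion.** The point holds as an omission with a conditional bias. The SAP plans Kaplan-Meier for states that partly exclude one another, leaves out the protocol's competing-risk analysis, and gives no rule for competing states or death. If other states are censored, the state risks are overstated, by at most 0.54 points in total and about 5% relative per state at the plan's 10% risk.

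A material error needs far more infection than planned. That is possible: SAP 3.5.1 counts diagnosis by symptoms, SAP 6.3.9 leaves the qualifying symptoms open, and time zero for controls is first known exposure (SAP 6.4.1), which SAP 6.6 allows to precede enrolment by more than three months. The documents give no such rate, so the 45.6% against 40% example rests on an assumed total, an assumed split and proportional cause-specific hazards.

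A reader might also infer that the primary result is at risk. It is not: this concerns descriptive and secondary absolute-risk curves, not the primary hazard ratio.

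**What to change.** In SAP 6.3:

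- Define each HCW's severity outcome by the worst state reached in follow-up and state which date counts as the event date, or use a multi-state model that allows progression from ambulatory to hospitalised. Do not let an earlier ambulatory state end the risk of hospitalisation.
- Reconcile the mild and severe definitions, here and in 3.5.2 and 6.5, so that no HCW meets both.
- Use Aalen-Johansen cumulative incidence for the severity states, with death and the mutually exclusive states as competing events.
- Keep Kaplan-Meier for all-cause death. For composite infection, treat death before infection as a competing event or state that it is negligible.

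In SAP 6.5, label the state-specific Cox results as cause-specific hazard ratios. In 6.4 and 6.5, carry over the competing-risk commitment of Protocol 8.7.4 or justify dropping it.

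The cost is SAP wording and a standard multi-state function in R. No new data are needed.

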This is an observational cohort study; therefore, no preventive interventions, visits or laboratory tests are mandated. Dosing and duration of potential prophylactic treatment is at the discretion of the institution and/or healthcare provider, in accordance with regular local practice. However, serology testing for SARS-CoV-2 antibodies are being offered to the first 50% of participating HCWs per country, at enrollment and at the last follow-up (i.e. at Week 12).

Figure 1: Healthcare Worker Flow – Study Schematic

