3.6.5 Other Covariates

- COVID-19 symptoms (and date the symptoms begin)
 - Fever (temperature over 38°C)
 - Subjective fever (felt feverish)
 - Chills
 - Myalgia (muscles hurt or ache)
 - Rhinorrhea (runny or drippy nose)
 - Pharyngitis (sore throat)
 - Cough (new onset or worsening of chronic cough)
 - Dyspnea (hard to breathe or difficulty breathing)
 - Pneumonia
 - Nausea or vomiting
 - Headache or migraine
 - Abdominal pain (pain in tummy)
 - Asthenia (weakness or loss of strength)
 - Arthralgia (joint pain)
 - Anosmia (loss of smell)

- Ageusia (loss of taste)
- Blue coloring in toes
- Diarrhea (two or more looser-than-normal stools in 24 hours)
- SARS-CoV-2 testing
 - Type of test, if known
 - PCR (positive/negative)
 - Antigen test (positive/negative)
 - Serology (IgG and/or IgM, positive/negative or titer)
 - Date of test
- Household history (COVID-19)
 - Number of household contacts
 - Additional household member(s) exposed to COVID-19 (yes/no). If yes, how many
 - Additional household member(s) with symptoms consistent with COVID-19 (yes/no). If yes, how many?
 - Additional household member(s) diagnosed with COVID-19 (yes/no). If yes, how many
- Healthcare worker-level covariates
 - Demographics at entry
 - Underlying conditions and key comorbidities
 - Job characteristics
 - Concomitant medications
 - Blood type
- Healthcare facility characteristics
 - Country, region
 - Urban or rural setting
 - Type of facility (public/private/community healthcare)
 - Teaching/university hospital or non-teaching
 - Capacity
 - number of patients tested for COVID-19
 - number of COVID-19 patients treated
 - number of hospitalized beds (overall, ICU, emergency department)
 - number of exposed HCWs
 - number of HCWs tested for COVID-19
 - Number of HCWs who developed confirmed or clinically diagnosed COVID-19
 - Number of HCWs who died from COVID-19
 - Approved PPE use policy, and experience of PPE shortage
 - Approved prophylactic treatment policy
 - Shortage of COVID-19 related tests
 - BCG vaccination policy
- Concomitant medications (other than for COVID-19)
 - Antibiotics (yes/no). If yes, please specify.

- Azithromycin
- Trimethoprim/sulphamethoxazole
- Macrolide antibiotics (roxithromycin, clarithromycin, erythromycin)
- Other antibiotics
- Antimalarials (yes/no). If yes, please specify.
 - Hydroxychloroquine
 - Chloroquine
 - Sulfadoxine-pyrimethamine (SP)
 - Other antimalarials
- Antiparasitics (yes/no). If yes, please specify.
 - Ivermectin(yes/no)

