6.3.9 COVID-19 symptoms

The distribution of COVID-19 symptoms will be displayed for the following time periods after first indication of symptoms:

- Symptoms at any time on or after first symptoms seen for the HCW
- Symptoms within 1 week after first symptoms seen for the HCW
- Symptoms within 1-2 weeks after first symptoms seen for the HCW
- Symptoms within 2-4 weeks after first symptoms seen for the HCW
- Symptoms >4 weeks after first symptoms seen for the HCW

A summary of the proportion of HCWs that had at least one symptom, at least two symptoms, at least three symptoms will also be displayed within these time periods. A histogram will be produced where the bins along the x-axis are the number of unique symptoms each HCW reports on their survey. This descriptive analysis will aid in determining which symptoms or group of symptoms will be considered for diagnosing HCWs as being COVID-19 infected.

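### SAP 6.3 widens the protocol's weekly rate of PCR-confirmed symptomatic COVID-19 to PCR-confirmed or symptomatic, gives no reason, and reports the protocol's measure nowhere else

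*SAP*

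**What the plan says.** Protocol 8.7.3 plans to tabulate, week by week and by facility, "The observed incidence weekly rates of PCR-confirmed symptomatic COVID-19 and of COVID-19-related hospitalizations and deaths", and to compare these rates by prophylactic exposure. Read plainly, a case in the first category needs both a positive PCR and symptoms.

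SAP 6.3 repeats the sentence with one word added: "The observed incidence weekly rates of PCR-confirmed or symptomatic COVID-19", followed by the same hospitalisation and death rates. It then specifies the comparison in more detail than the protocol does: prophylaxis yes or no, by individual treatment, and by use before or after exposure to COVID-19 patients, the last two subject to sample size. It gives no reason for the added word.

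Three other places bear on what the union contains:
- SAP 3.1 states that "no preventive interventions, visits or laboratory tests are mandated".
- SAP 3.6.5 lists 18 self-reported symptoms. Some are fairly specific, such as loss of smell. Others are common complaints, such as runny nose, sore throat, headache and diarrhoea.
- SAP 6.3.9 says that the symptom description "will aid in determining which symptoms or group of symptoms will be considered for diagnosing HCWs as being COVID-19 infected", so no qualifying rule exists yet.

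**The concern.** The two sentences define different quantities. The protocol's rate is narrow and laboratory-anchored. The SAP's rate can be met by a positive PCR alone or by symptoms alone, including symptoms in someone never tested or tested negative. Reported under nearly the same label, it could be taken for the protocol's measure.

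Two things are at stake. First, the registry would not report an incidence that its protocol says it will report. Second, SAP 6.3 compares the rate across prophylaxis groups. If many counted cases are not SARS-CoV-2 infections, that comparison says less about prophylaxis, and the reader cannot tell how much less.

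**Working it through.** **Text comparison.** Let P be a positive PCR and S be symptomatic.
- Protocol 8.7.3: P and S.
- SAP 6.3: P or S. This adds two groups: P without S, and S without P (untested or PCR-negative).

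**Is the intersection recovered elsewhere in the SAP?** No.
- SAP 6.7 re-runs the primary analysis under four single definitions. Positive test only ignores symptoms, and symptoms only ignores the test.
- The test component in SAP 3.5.1 is any positive test. SAP 3.6.5 records PCR, antigen and serology, so that component is not PCR-specific.
- SAP 6.7 applies to the primary analysis, not to weekly rates by facility.

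**Does the protocol version explain it?** Probably not. SAP 1 is based on protocol 1.0 and the current protocol is 1.1. Amendment 1's list of revised Research Methods sections does not include 8.7.3. The log also notes minor language edits that it does not summarise, so this is an indication and not proof.

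**Size, as an illustration.** The documents give no figure for this rate, so there is none to reproduce.
- From Protocol 8.7.7 and SAP 5: unexposed risk over the study period 0.10, relative risk (RR) 0.78, hence exposed risk 0.10 × 0.78 = 0.078.
- Assumed: a share f of uninfected HCWs is counted on symptoms alone, equal in both groups, and every true infection is counted.
- Apparent unexposed risk = 0.10 + 0.90f.
- Apparent exposed risk = 0.078 + 0.922f.
- Share of counted unexposed cases that are true infections = 0.10 / (0.10 + 0.90f).

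| f | Unexposed | Exposed | Apparent RR | True share, unexposed |
|---|---|---|---|---|
| 0 | 0.100 | 0.078 | 0.78 | 100% |
| 2% | 0.118 | 0.0964 | 0.817 | 85% |
| 5% | 0.145 | 0.1241 | 0.856 | 69% |
| 10% | 0.190 | 0.1702 | 0.896 | 53% |
| 20% | 0.280 | 0.2624 | 0.937 | 36% |

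These are cumulative risks over the study period, not weekly rates. They show direction and order of size only.

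**The case against.** The strongest reply is that the word was added on purpose and properly. Protocol 8.7.1 leaves outcome variables, including confirmed versus clinically diagnosed, to the SAP. The SAP's primary outcome (3.5.1) is a composite that accepts symptoms, and SAP 6.3.5 again pairs confirmed with symptomatic disease. With testing optional and test shortages recorded by facility, a PCR-only rate by facility would partly track access to tests. All of this stands as a reason to show the broader rate. It does not explain why the rate that Protocol 8.7.3 names is dropped without comment.

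Three stronger readings are tempting, and the documents do not support them.
- *That a laboratory-confirmed endpoint goes unanalysed.* PCR-confirmed symptomatic COVID-19 is not among the outcomes in Protocol 8.1.1 or 8.1.2. It appears only in a descriptive tabulation, and positive-test infection is analysed in SAP 6.7.
- *That any HCW with a runny nose becomes a case.* The symptoms in SAP 3.6.5 are variables to be collected, not a case definition. The rule foreseen in SAP 6.3.9 may be narrower. What can be said is that none is fixed now.
- *That the rates would mostly reflect ordinary complaints and the contrast would nearly vanish.* This needs a high f, and the documents give no value for it. Some symptom-only cases will be true untested infections, which do not dilute.

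The equal-f assumption can also fail in the other direction. SAP 3.5.2 and 3.6.5 count drugs such as azithromycin, when recorded as concomitant medication, as prophylaxis. A respiratory complaint could then make the same person both exposed and a case, and the bias need not be toward the null.

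**Conclusion.** The mismatch between Protocol 8.7.3 and SAP 6.3 is real, unexplained, and not made good elsewhere in the SAP. It concerns one descriptive rate. The primary hazard ratio and its positive-test-only sensitivity analysis do not depend on it. The change may be deliberate, but the SAP does not say so.

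The consequence is a weekly rate, compared by prophylaxis, that is less specific than the one planned and rests on a symptom rule not yet set. With f from 5% to 20% and equal in both groups, a true ratio of 0.78 would appear as 0.86 to 0.94. At f = 2% it would appear as 0.82. Those values rest on the plan's 10% risk, the assumed f, and complete counting of true infections. The point deserves correction before analysis but does not threaten the primary analysis.

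**What to change.** In SAP 6.3:
1. Report the weekly rate of PCR-confirmed symptomatic COVID-19 as the protocol states, defined as a positive PCR plus a qualifying symptom within a pre-specified window around the test date.
2. Show the PCR-confirmed or symptomatic rate as a separate, labelled row, using a symptom rule fixed before results are compared by prophylaxis.
3. If the broader measure is meant to replace the protocol's, say so and give the reason. Protocol 8.7 requires deviations from planned analyses to be described and justified in the final report.

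Adding the strict definition to the list in SAP 6.7 is optional; the protocol does not ask for it there.

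The cost is one sentence, one derived variable and one table row. Protocol Appendix 2 already collects PCR result, test date and symptom onset at enrollment and weekly. The strict row will have fewer events, and HCWs without access to PCR cannot enter it, so it should be read alongside the facility-level data on test shortage.
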